5.3.1 Rationale for Dose Titration

Dose titration has been added because data from the GBT440-001 study has shown a linear and highly significant relationship between GBT440 blood level and improvement in hemolysis and no plateau effect has been reached. This suggests that subjects may derive greater benefit at higher doses achieving higher haemoglobin occupancy. Furthermore the target for optimal efficacy based on individuals with HbS/Hereditary persistence of fetal haemoglobin is 20-30% haemoglobin occupancy (Ngo 2011) and the preliminary PK data from Cohort 17 showed that the majority of subjects did not maintain haemoglobin occupancy >20% at 900 mg daily dosing. In addition, no dose limiting toxicities or concerning dose-or exposure related toxicities pose a safety concern with higher doses. Doses of 1000 mg for 28 days and 900 mg for 90 days have been well tolerated, with the majority of AEs were Grade 1 or 2 in severity. At 1500 mg, the predicted C_{max} is 167 μ g/mL, which is less than the C_{max} already observed and found to be well-tolerated in healthy volunteers in GBT440-001 (294 μ g/mL at 900 mg [Cohort 10]).

To assess the higher dose of 1500 mg, subjects will be dose escalated by 300 mg over 2-week intervals. The principal investigator will determine if the 600 mg or the 900 mg dose is well tolerated (after at least 28 days of prior dosing), and that the subject may receive further benefit from higher dosing (further improvement in haemoglobin, reticulocyte count or unconjugated bilirubin) the dose may be increased by one capsule (300 mg) every two weeks up to a maximum of 1500 mg.

This study will be performed in compliance with the protocol, ICH GCP and applicable regulatory requirements. Aspects of the study concerned with the investigational medicinal product(s) (IMPs) will meet the requirements of EU GMP.

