8.2.1 Dose Titration

Provided the Principal Investigator determines that the 600mg dose (in Cohort 15), 900 mg dose (in Cohort 17), and 900 mg dose in the Cohorts 7, 11, 12, 14, 16 or 17 is well tolerated (after at least 28 days of dosing), and that the subject may receive further benefit from higher dosing (further improvement in haemoglobin, reticulocyte count or unconjugated bilirubin) the dose may be increased by one capsule (300 mg) every two weeks up to a maximum of 1500 mg dose.

When increasing the dose, the subject should return to clinical every 2 weeks for Laboratory and AE assessments

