17.0 STUDY SCHEDULE

Table 4 Schedule of Assessments Group 1

Group 1: Subjects from Cohort 17 in the GBT440-001 study who have received GBT440 900mg per day for 4 months will continue receiving GBT440 900 mg per day for a further 2 months.

Assessments	Enrolment	Outpatient Treatment Period							
		1 a	15 +/-3 days g	30 +/-3 days	45 +/-3 days g	60 +/-3 days	67 +/-3 days	74 +/-5 days	88 end
Visit number	0	1		2		3	4	5	6
Informed consent	X	X							
Eligibility assessment	X	X							
Medical History	X								
Physical examination b	X		X	X	X				X
Weight	X		X	X	X	X			X
Vital signs	X	X	X	X	X	X			X
12 Lead ECG (single) c				X		X			X
Drug administration d		X				X			
Adverse events		X-----							-X
Urinalysis e	X		X		X				X
Urine microalbumin/creatinine	X								X
Haematology e	X		X	X	X				X
Serum biochemistry e	X		X	X	X				X
Coagulation e	X		X		X				X
Pregnancy test (females only)	X			X		X			X
Haemoglobin electrophoresis									X
PK samples (plasma and whole blood) f	X			X		X	X	X	X
Serum erythropoietin	X ^h			X		X			X
Exploratory plasma biomarkers	X ^h			X		X			X
Dense cells	X ^h			X		X			X
Carboxyhaemoglobin	X ^h								X
HbA1c	X ^h								X
NT-proBNP	X ^h								X
Concomitant medication diary	X-----								-X

Key

- a: Enrolment and visit 1 may be combined. On admission to the clinic the subjects will be asked whether they want to be considered for study GBT440-024. If the subject is interested in being enrolled on study GBT440-024 all consent activities will be completed before the samples/procedures for GBT440-001 or GBT440-024 are collected/Performed. Visit 0 (enrolment visit) is the last day of treatment in GBT440-001, which can be 6 days before Visit 1. If the last day of treatment in GBT440-001 (Day 118 or Day 60 for Cohort 17 and Cohort 15) – the enrolment visit is not being repeated as standalone visit.
- b: Complete physical examination on enrolment, a limited physical examination on all other days. Directed physical examinations will be performed as required.
- c: 12 lead ECG (single) will be performed within 30 minutes prior to dose
- d: GBT440 900 mg(three capsules) will be administered daily in the morning. On days when PK samples are drawn GBT 440 should be administered after an overnight fast.

During the dosing period subjects will be contacted every week in between out-patient visits to confirm GBT440 administration and subject well -being.

- e: Additional samples will be collected if clinically indicated

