- f: PK samples will be drawn pre dose. If the dose is increased to 1500 mg, please collect the following timepoints: pre dose, then 1-4 hours, 6-8 hours and 24 hours post dose on study visit days of Day 15 (± 3 days), Day 60 (± 3 days) and Days 90 (± 3 days) of receiving 1500 mg.g: Days 15 and 45 are only to be conducted if the dose is increased to 1500 mg.
- h: Can be omitted if measurements were collected in the past 7 days as part of the GBT440-001 study.

Table 5 Schedule of Assessments for Groups 2, 4 and 5

Groups 2: Subjects from Cohort 17 in the GBT440-001 study who have received placebo for 4 months will receive GBT440 900mg per day for 6 months

Group 4: Subjects from Cohort 15 in the GBT440-001 study who have received placebo for 2 months will receive GBT440 900 mg per day for 6 months

Group 5: Subjects with SCD from Cohorts 7, 11, 12, 14, 16 or 17 in the GBT440-001 study will receive GBT440 900 mg per day for 6 months

Assessments	Enrolment a	Baseline for Cohort 7,11,12,14, 16 or 17 (within 7 days of Day 1)	Outpatient Treatment Period											
			1 +/-3 days a	15 +/-3 days	30 +/-3 days	45 +/-3 days	60 +/-3 days	90 +/-3 days	120+/-3 days	150+/-3 days	180 +/-3 days	187+/-3 days	194 +/-5 days	208 End
Day number	Last treatment day GBT440-001 (+6 days) Cohorts 15 and 17													
Visit number	0		1	2	3	4	5	6	7	8	9	10	11	12
Informed consent	X	X												
Eligibility assessment	X	X												
Medical History	X	X												
Physical examination b	X	X		X	X		X	X	X	X	X			X
Weight	X	X		X	X	X	X	X	X	X	X			X
Vital signs	X	X	X	X	X	X	X	X	X	X	X			X
12 Lead ECG (single) c	X	X			X		X	X	X	X	X			
Drug administration d				X-----							X			
Adverse events				X-----										X
Urinalysis e	X	X						X	X	X	X			X
Urine microalbumin/creatinine	X	X						X			X			
Haematology e	X	X		X	X	X	-	X	X	X	X			X
Serum biochemistry e	X	X		X	X	X	X	X	X	X	X			X
Coagulation e	X	X		X		X		X	X	X	X			X
Pregnancy test (females only)	X	X			X		X	X	X	X	X			X
Haemoglobin electrophoresis		X						X			X			X
PK samples (plasma and whole blood) f	X			X	X		X	X	X	X	X	X	X	X
Serum erythropoietin	X ^h	X			X		X	X	X	X	X			X
Exploratory plasma biomarkers	X ^h	X			X		X	X	X	X	X			X

Assessments	Enrolment a		Outpatient Treatment Period											
			1 +/-3 days	15 +/-3 days	30 +/-3 days	45 +/-3 days	60 +/-3 days	90 +/-3 days	120+/-3 days	150+/-3 days	180 +/-3 days	187+/-3 days	194 +/-5 days	208 End

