Day number	Last treatment day GBT440-001 (+6 days) Cohorts 15 and 17	Baseline for Cohort 7,11,12,14, 16 or 17 (within 7 days of Day 1)	a											
Dense cells	X ^h	X			X		X	X	X	X	X			X
Carboxyhaemoglobin	X ^h	X						X			X			X
HbA1c	X	X						X			X			X
NT-proBNP	X ^h	X						X			X			X
Concomitant medication diary		X	X-----											X

Key

Note: Visit 0 is the last treatment day for subjects in GBT-440-001 (Day 118 for Cohort 17 and Day 60 for Cohort 15)

- a: Enrolment and visit 1 may be combined. On admission to the clinic the subjects will be asked whether they want to be considered for study GBT440-024. If the subject is interested in being enrolled on study GBT440-024 all consent activities will be completed before the samples/procedures for GBT440-001 or GBT440-024 are collected/Performed. Visit 0 (enrolment visit) is the last day of treatment in GBT440-001, which can be 6 days before Visit 1. If the last day of treatment in GBT440-001 (Day 118 or Day 60 for Cohort 17 and Cohort 15) – the enrolment visit is not being repeated as standalone visit.
- b: Complete physical examination on enrolment, a limited physical examination on all other days. Directed physical examinations will be performed as required.
- c: 12 lead ECG (single) will be performed within 30 minutes prior to dose
- d: GBT440 900mg(three capsules) for Group 2 and GBT 440 600mg (2 capsules) for Group 4 and GBT440 900 mg (3 capsules) for Group 5 will be administered daily in the morning. On days when PK samples are drawn GBT 440 should be administered after an overnight fast.
- During the dosing period, subjects will be contacted every week in between outpatient visits to confirm GBT440 administration and subject well being.
- e: Additional samples will be collected if clinically indicated
- f: PK samples will be drawn pre dose. If the dose is increased to 1500 mg, please collect the following timepoints: pre dose, then 1-4 hours, 6-8 hours and 24 hours post dose on study visit days of Day 15 (±3 days), Day 60 (±3 days) and Days 90 (±3 days) of receiving 1500 mg.
- h: Can be omitted if measurements were collected in the past 7 days as part of the GBT440-001 study.

Table 6 Schedule of Assessments Group 3

Group 3: Subjects from Cohort 15 in the GBT440-001 study who have received GBT440 600 mg per day for 2 months will continue receiving GBT440 600 mg per day for a further 4 months (the dose may be increased if the subject tolerated 600 mg in GBT440-001).

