- e: PK samples will be drawn pre dose. . If the dose is increased to 1500 mg, please collect the following timepoints: pre dose, then 1-4 hours, 6-8 hours and 24 hours post dose on study visit days of Day 15 (± 3 days), Day 60 (± 3 days) and Days 90 (± 3 days) of receiving 1500 mg.
- f: Days 45 are only to be conducted if the dose is increased to 1500 mg.
- g: Can be omitted if measurements were collected in the past 7 days as part of the GBT440-001 study.

[figure not shown]

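### Section 8.2.1 asks for two-weekly laboratory visits whenever the dose is raised, but Tables 4 and 6 hold the interim visits only at 1500 mg; Table 4 also asks Group 1 for two 1500 mg PK profiles that fall after its last dose.

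*Combined protocol and SAP*

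**What the plan says.** Section 8.2.1 sets the titration rule: "the dose may be increased by one capsule (300 mg) every two weeks up to a maximum of 1500 mg dose". It adds: "When increasing the dose, the subject should return to clinical every 2 weeks for Laboratory and AE assessments". No dose threshold is attached to that sentence.

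The schedules in Section 17.0 attach one. Table 4 (Group 1), footnote g: "Days 15 and 45 are only to be conducted if the dose is increased to 1500 mg". Table 6 (Group 3), key: "f: Days 45 are only to be conducted if the dose is increased to 1500 mg". Table 6 has no Day 15 column. Table 5 (Groups 2, 4 and 5) lists Days 15 and 45 without any condition.

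For PK, all three tables use the same instruction once a subject reaches 1500 mg: pre-dose and three post-dose samples on "Day 15 (± 3 days), Day 60 (± 3 days) and Days 90 (± 3 days) of receiving 1500 mg". Group 1 "will continue receiving GBT440 900 mg per day for a further 2 months", and Table 4 ends drug administration at Day 60. Table 6 ends it at Day 120 and Table 5 at Day 180.

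On when the first increase may occur, Section 5.3.1 refers to the "600 mg or the 900 mg dose is well tolerated (after at least 28 days of prior dosing"), and the Table 6 heading says "the dose may be increased if the subject tolerated 600 mg in GBT440-001". Section 8.2.1 itself asks for at least 28 days of dosing without saying in which study.

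**The concern.** Two instructions on safety visits differ, and Section 15.2 tells sites to follow the protocol exactly. The difference bites for Group 1 at 1200 mg and Group 3 at 900 or 1200 mg. The highest repeated daily dose that Section 5.2.1 reports in SCD subjects is 1000 mg, so 1200 mg is already above prior experience. Section 5.3 relies on haemoglobin, reticulocyte and erythropoietin monitoring to detect hypoxia or hyperviscosity, and Section 8.2 stops dosing when haemoglobin exceeds 12.8 g/dL. A site working from Table 4 or 6 alone would miss haemoglobin values that feed that rule.

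Table 4 is also circular. Group 1 cannot reach 1500 mg before about Day 15, yet the Day 15 visit that should inform that step is held only if the step is taken.

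The PK instruction has a simpler fault: the same text sits in schedules with 60, 120 and 180 days of dosing, and in the shortest it cannot be carried out.

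**Working it through.** **Inputs.** Step 300 mg every 14 days, maximum 1500 mg (Section 8.2.1). Group 1: starts at 900 mg, last dose Day 60 (63 with the window), study end Day 88 (Table 4). Group 3: starts at 600 mg, last dose Day 120 (123 with the window) (Table 6). The plan gives no figure to reproduce; this is calendar arithmetic.

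**Laboratory gap below 1500 mg, tables alone.** In Table 6 the unconditional on-treatment haematology days are 30, 60, 90 and 120.
- Group 3, 900 mg on Day 1 and 1200 mg on Day 15: first haematology Day 30, so 30 − 1 = 29 days, with two increases in between.
- Group 3, increase at the Day 30 visit: 60 − 30 = 30 days.
- Group 1, 1200 mg on Day 1 and held there: 30 − 1 = 29 days.
- Section 8.2.1 interval: 14 days.

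The Day 1 increases assume that dosing in GBT440-001 counts toward the 28 days. If it does not, Group 3 steps fall on Days 29, 43 and 57. The last two lie between the Day 30 and Day 60 samples, so the conflict remains.

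**PK profiles.** Study day of the Nth day on 1500 mg = start + N − 1.

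| Path | 1500 mg starts | Day 15 | Day 60 | Day 90 | Last dose |
|---|---|---|---|---|---|
| Group 1, earliest | 15 | 29 | 74 | 104 | 60 |
| Group 1, every window stretched | 12 | 23 | 68 | 98 | 63 |
| Group 1, prior dosing not counted | 43 | 57 | 102 | 132 | 60 |
| Group 3, earliest | 29 | 43 | 88 | 118 | 120 |
| Group 3, prior dosing not counted | 57 | 71 | 116 | 146 | 120 |

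In Group 1 only the first profile is ever on treatment. In Group 3 the Day 90 profile is on drug only if 1500 mg starts by 120 − 89 = Day 31 (123 − 89 + 3 = Day 37 with windows). In Table 5 all three are on drug if 1500 mg starts by 180 − 89 = Day 91.

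**Subjects exposed.** Group 3: Section 5.2.1 has one Cohort 15 subject dosed and 7 to follow. Assuming the 3:1 split of Cohorts 7, 11, 14 and 16, 7 × 0.75 = 5.25 and 8 × 0.75 = 6, so about 5-6.

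Group 1: Section 5.2.1 shows two Cohort 17 subjects ongoing and two enrolled here by 3 August 2016. Assume the two enrolled had Day 1 by 9 August (3 August plus the 6 days allowed). Then Version 2 (28 September) fell on their Day 51 and Day 60 was 7 October. A first increase on 28 September puts both the two-week visit and the earliest 1500 mg dose on 12 October (Day 65), after the last dose. They are therefore outside both problems. That leaves at most the two ongoing subjects, fewer if either was on placebo and so enters Group 2.

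**The case against.** The strongest defence is that the texts are complementary: Section 8.2.1 ties visits to the date of an increase, while the footnotes only decide whether fixed study-day columns are used. Leaving a column unused does not cancel a visit required elsewhere. This stands to the extent that a site following Section 8.2.1 holds the visits and loses nothing. It does not remove the fault: the footnotes limit the visits to 1500 mg without pointing to Section 8.2.1, and Table 5 schedules the same days unconditionally.

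Other safeguards also count: weekly contact, clinically indicated extra samples (Table 4 footnote e), discretionary repeat testing (Section 9.5) and SMC review at least monthly (Section 7.1). They reduce the risk but do not supply a haemoglobin value at two weeks.

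On PK, the defence largely succeeds on impact. Days that never occur on 1500 mg generate no samples, the objective is only to observe PK, and Section 12.3 is descriptive. Table 4 keeps the Day 60 pre-dose sample and the Day 67, 74 and 88 washout samples.

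A reader might infer that subjects are escalated without laboratory monitoring, or that the PK objective fails in Group 1. The documents support neither. Nor should weight be put on the apparently empty Day 60 haematology cell in Table 4, which may be a table-conversion fault.

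**Conclusion.** Wrong as written, with modest impact; it should be corrected. The main point is the visit conflict: a literal reading of Tables 4 and 6 lengthens the laboratory interval after an increase from 14 days to 29-30 days at doses below 1500 mg. It concerns mainly Group 3, about 5-6 subjects on an assumed 3:1 split, plus at most about 2 in Group 1. These are ceilings, since not all will enrol or be titrated.

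The unreachable Day 60 and Day 90 profiles in Group 1 are secondary: certain on every permitted path, but relevant to 0-2 subjects. Group 1 loses the later serial profiles at 1500 mg, not its trough and washout data.

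The day-by-day gaps after a Day 1 increase depend on prior GBT440-001 dosing counting toward the 28 days. Both faults persist if it does not. The Group 1 count depends on the assumed Day 1 date for the two subjects already enrolled.

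**What to change.** **Visits.** In the Table 4 and Table 6 footnotes, change the condition to any increase above the starting dose (900 mg and 600 mg respectively). Add a conditional Day 15 laboratory and AE visit to Table 6. State in all three tables that the two-weekly visits of Section 8.2.1 apply after any increase at any time, because fixed Day 15 and 45 columns miss increases made at later visits. Correct the Table 6 key: the Day 45 column is marked g but its condition sits under f.

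**PK.** In Table 4, keep the profile at Day 15 of 1500 mg and replace the Day 60 and Day 90 targets with one profile at the last on-treatment visit (Day 60). The Day 15 window runs from start + 11 to start + 17. Starts on Days 15-42 then give two profiles, starts on Days 43-49 give one Day 60 profile inside that window, and later starts give Day 60 only. In Tables 5 and 6, replace any target after the last dose with the last on-treatment visit (Day 180 or Day 120).

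**Cost.** Footnote edits and one conditional column. Each added visit is one Section 8.2.1 already calls for: 3.5 + 2.0 = 5.5 mL of blood, or 7.3 mL with the 1.8 mL coagulation sample kept as tabulated, when the physical examination and urinalysis listed for those days would also apply. For few or no Group 1 subjects there are three extra post-dose PK samples (3 × 2.0 = 6 mL) and a return for the 24-hour sample.

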9.0 STUDY PROCEDURES

Table 2 Estimated Blood Volumes:

Assessment	Sample Volume (mL)	No. of Samples	Total Volume (mL)
Sickle Cell Disease Subjects: Multiple Dose			
Safety			
Serum Biochemistry	3.5	Up to 10	35.0
Coagulation	1.8	Up to 8	14.4
Haematology	2.0	Up to 10	20.0
Pregnancy	3.5	8	28.0
Hba1c	3.5	7	24.5
Pharmacokinetic			
GBT440	2.0	11	22.0
Pharmacodynamic			
Serum erythropoietin (EPO)	3.5	Up to 8	28.0

Assessment		Sample Volume (mL)	No. of Samples	Total Volume (mL)
	Frozen Plasma Reserved for immunology/inflammation and exploratory markers	5.0	Up to 8	40.0
	Haemoglobin electrophoresis	2.0	Up to 4	8.0
	Carboxyhaemoglobin	2.0	Up to 7	14.0
Disease Related				
	Dense Cells	2.0	Up to 8	16.0
	NT pro-BNP	2.0	Up to 8	16.0
Total [b]				335.9

Sample volumes are based on direct venipuncture.

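### Table 5 omits haematology at Day 60, leaving stable-dose subjects in Groups 2, 4 and 5 without a scheduled haemoglobin or reticulocyte count from Day 45 to Day 90

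*Combined protocol and SAP*

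**What the plan says.** Table 5 in Section 17.0 sets the visits for Groups 2, 4 and 5. Its haematology row is "Haematology e X X X X X - X X X X X" (blank cells drop out of the quotation). The five marks before the dash are enrolment, baseline and Days 15, 30 and 45; the five after it are Days 90, 120, 150, 180 and 208. The dash therefore sits at Day 60.

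The next row, "Serum biochemistry e X X X X X X X X X X X", has the same pattern but is marked at Day 60. So is the erythropoietin row, "Serum erythropoietin X ^h X X X X X X X X". PK, exploratory biomarkers and dense cells are also taken that day; haemoglobin electrophoresis is not.

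Other parts of the protocol that bear on this:

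- Table 3 (Section 9.5) places haemoglobin and the reticulocyte count in the haematology panel.
- Section 5.3 says haemoglobin, reticulocytes and erythropoietin will be watched for signs of tissue hypoxia or hyperviscosity.
- Section 8.2 requires dosing to stop if haemoglobin exceeds 12.8 g/dL.
- Section 8.2.1 calls for laboratory visits every two weeks while the dose is being raised.
- Footnote e to Table 5 adds only this: "Additional samples will be collected if clinically indicated". The notes to Table 3 leave further testing to the Investigator's discretion.
- The blood-volume table in Section 9.0 lists "Haematology 2.0 Up to 10 20.0" and "Serum Biochemistry 3.5 Up to 10 35.0".

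**The concern.** A site works from the schedule table. Followed as printed, it draws blood from a stable-dose subject at Day 60 and obtains erythropoietin without the haemoglobin and reticulocyte values that Section 5.3 names alongside it. The haemoglobin stopping threshold then has no routine value to act on between Day 45 and Day 90. Physical examination, ECG, biochemistry and weekly contact continue, but none of them measures haemoglobin.

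The gap also touches a secondary objective. Section 9.2.1 lists haemoglobin and reticulocytes as haemolysis markers, and Section 12.4 summarises these markers by time point. At Day 60, stable-dose subjects in these groups would contribute bilirubin, LDH and dense cells but not the other two.

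**Working it through.** **1. Scheduled samples against the blood-volume table.** Inputs are the Table 5 rows and the sample numbers in Section 9.0. The count is one pre-dose draw (enrolment or baseline) plus every post-dose mark.

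| Assessment | Table 5 | Blood-volume table |
|---|---|---|
| Haematology | 1 + 8 = 9 | 10 |
| Serum biochemistry | 1 + 9 = 10 | 10 |
| Coagulation | 1 + 7 = 8 | 8 |
| Pregnancy test | 1 + 7 = 8 | 8 |
| PK | 1 + 10 = 11 | 11 |
| Erythropoietin | 1 + 7 = 8 | 8 |
| Exploratory plasma | 1 + 7 = 8 | 8 |
| Haemoglobin electrophoresis | 1 + 3 = 4 | 4 |
| Dense cells | 1 + 7 = 8 | 8 |
| HbA1c | 1 + 3 = 4 | 7 |
| Carboxyhaemoglobin | 1 + 3 = 4 | 7 |
| NT-proBNP | 1 + 3 = 4 | 8 |

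The plan's figure of 10 for haematology is not reproduced from the row as printed. With Day 60 marked it is: 1 + 9 = 10. Of the 11 other rows, 8 agree. That 8 is a maximum across groups: PK has no baseline mark (Group 5 gets 10) and electrophoresis has no enrolment mark (Groups 2 and 4 get 3), so any one subject matches 7.

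**2. Rival count.** Counting enrolment and baseline as two draws gives haematology 8 + 2 = 10 without Day 60. But biochemistry then becomes 11 against 10, coagulation 9 against 8 and erythropoietin 9 against 8, so this reading does not fit.

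**3. Haematology gap, stable dose.** Days after enrolment or baseline: 15, 30, 45, 90, 120, 150, 180, 208.

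- Nominal: 90 − 45 = 45 days.
- With ±3-day windows: 87 − 48 = 39 to 93 − 42 = 51 days.
- Share of treatment: 45/180 = 25%.
- Next longest interval: 30 days.

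**4. Visits with haemoglobin, reticulocytes and erythropoietin together.** These are Days 30, 90, 120, 150, 180 and 208. The first interval is 90 − 30 = 60 days (87 − 33 = 54 to 93 − 27 = 66); on treatment they are 30 days apart after that.

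**5. With Day 60 marked.** The Day 45 to 90 gap splits into 15 and 30 days. The longest interval between on-treatment visits, for haematology and for complete sets, becomes 90 − 60 = 30 days (87 − 63 = 24 to 93 − 57 = 36).

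**6. Table 4 (Group 1), as the table could be read.** The row is "Haematology e X X X X X", which aligns to enrolment and Days 15, 30, 45 and 88. Its footnote g says "Days 15 and 45 are only to be conducted if the dose is increased to 1500 mg". A Group 1 subject not being titrated would have enrolment, Day 30 and Day 88 only: 88 − 30 = 58 days (88 − 33 = 55 to 88 − 27 = 61, as Day 88 has no printed window). Dosing ends at Day 60, so the last 60 − 30 = 30 dosing days would have no scheduled count. This depends on the cell alignment and is a point to check.

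**The case against.** **The dash may not be the plan's.** Tables read from a PDF can be damaged, and Table 6 shows a column misalignment. A mis-rendered X would also explain a budget of 10 against a row of 9. This stands as a caveat. Even so, the dash is a printed character where other empty cells in the row are blank, and checking the source settles the matter. Table 6 (Group 3), lined up by its visit-number row, appears to schedule haematology at Day 60.

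**The blood-volume table is weak evidence.** Its 10 is an upper limit, three rows miss by 3 or 4 samples, and its listed volumes add to 265.9 mL against a printed total of 335.9 mL. That is fair. It supports the view that the dash is a slip, but the gap itself comes from Table 5 alone.

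**Few subjects are exposed and other safeguards exist.** Titration can begin after 28 days and brings two-weekly laboratory visits; enrolment is capped at 16 over three schedules, and the number held at a stable dose is unknown. LDH, bilirubin, dense cells, ECG and examination remain at Day 60, and a worrying result can prompt a blood count. All true, but those routes are reactive and schedule nothing. The two-weekly visits apply while the dose is rising; the fastest route from 900 to 1500 mg ends at about Day 28 + 14 = 42, and Section 8.2.1 does not say they continue afterwards.

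**Pairing and committee review.** Section 5.3 does not demand same-day draws, and Table 5 takes haematology without erythropoietin at Days 15 and 45. The Safety Monitoring Committee reviews cumulative data at least monthly, not a new haemoglobin per subject, and even a corrected interval could reach 36 days. These points weaken the arguments from complete sets and from monthly review. They do not supply the missing haemoglobin.

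**Conclusion.** The concern holds. As printed, Table 5 leaves a stable-dose subject in Group 2, 4 or 5 with no scheduled haemoglobin or reticulocyte count for 45 days (39 to 51), against 30 days for the next longest interval, although blood is drawn in the middle of that period. The schedule therefore falls short of the monitoring in Section 5.3 and gives the Section 8.2 stopping threshold nothing routine to act on.

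This assumes that the dash means no sample, that the subject is not being titrated, and that no unscheduled test is ordered. Nothing in the protocol shows that haemoglobin would pass 12.8 g/dL in this window; the point is that a planned safety check is absent. That the dash is a slip is likely but not proven. The Group 1 figure is conditional on confirming the Table 4 cell.

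**What to change.** Mark haematology X at Day 60 in Table 5, so that haemoglobin and reticulocytes are drawn with the erythropoietin already scheduled. Check the Day 60 haematology cell in Table 4 against the source table and mark it X if it is blank there too.

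The cost is one table cell, or two, and 2 mL of blood at a visit where blood is already taken. For Table 5 the extra sample is within the existing allowance: 10 × 2.0 mL = 20.0 mL.
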